# **Study Title**

Intravenous hydrogen nanobubbles effect on cardiac physiology and quality of life: a single blind, dose-response study

# **Study Design**

This study is a randomized, single-blind, dose-response clinical trial conducted to assess the effects of intravenous hydrogen nanobubbles (HNBs) on multiple health outcomes, including cardiac physiology, quality of life, and blood biomarkers. Participants were randomly assigned to one of six groups and received either HNB infusion or normal saline (control) over a 5-week period (10 sessions total, twice per week). The intervention doses were 0 mL (control), 5 mL, 10 mL, 15 mL, 20 mL, and 25 mL of HNB diluted in 500 mL of normal saline.

### **Ethical Considerations**

This study followed the ethical principles outlined in the Declaration of Helsinki. Ethical approval was granted by the Research Ethics Committee of State Polytechnic of Health Malang (Ref: 410/KPEK-POLKESMA/2022). All participants provided written informed consent, and participation was entirely voluntary. Blinding was maintained by using indistinguishable infusions for HNB and saline solutions.

# **Eligibility Criteria**

Inclusion criteria: adults aged 18–65 years, stable health condition permitting participation, and ability to provide informed consent.

Exclusion criteria: known allergies to hydrogen, concurrent participation in other trials, congestive heart failure, stage 4 or higher kidney disease, or liver failure.

### **Intervention Details**

Group A (Control): 500 mL normal saline

Group B: 5 mL HNB in 500 mL NS Group C: 10 mL HNB in 500 mL NS Group D: 15 mL HNB in 500 mL NS Group E: 20 mL HNB in 500 mL NS Group F: 25 mL HNB in 500 mL NS

Each group received 10 intravenous sessions over 5 weeks (2 sessions/week).

### **Outcome Measures**

Primary outcomes were assessed at baseline (week 0) and post-intervention (week 5):

- 1. Cardiovascular physiology: systolic and diastolic blood pressure (mmHg), heart rate (bpm), LVMI (g/m²), RWT (unitless), TAPSE (cm), and FMD (% change).
- 2. Quality of Life: measured using the SF-36 questionnaire.
- 3. Blood profile: inflammatory markers, lipid profile, liver function tests, and hematologic indices.

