## **Statistical Analysis Plan**

Statistical analyses were conducted to evaluate time-related changes and dose-dependent effects.

- Repeated Measures ANOVA was used to assess within-subject changes (pre- vs post-treatment) and interaction effects between dose and time.
- The Bayesian paired t-test was applied to complement the ANOVA results, providing Bayes Factors ( $BF_{10}$ ) that quantify the strength of evidence supporting the treatment effect.
- A p-value < 0.05 was considered statistically significant. BF10 values > 3 indicated moderate evidence, > 10 strong evidence, and > 100 very strong evidence for the alternative hypothesis.
- Data analysis was performed using appropriate statistical software, and each outcome was treated independently without aggregation into composite indices.

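### Liver tests and haematologic indices are read only through group mean change, so one or two marked individual changes at the top dose would usually meet none of the plan's evidence thresholds; by-dose descriptive tables should be added.

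*Combined protocol and SAP*

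**What the plan says.** Outcome Measures lists three domains of primary outcome, measured at week 0 and week 5. The third is "Blood profile: inflammatory markers, lipid profile, liver function tests, and hematologic indices". No analyte, unit, reference range or direction of harm is named.

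The Statistical Analysis Plan gives the same methods for every outcome: "Repeated Measures ANOVA was used to assess within-subject changes (pre- vs post-treatment) and interaction effects between dose and time", and "The Bayesian paired t-test was applied to complement the ANOVA results". The decision rules are "A p-value < 0.05 was considered statistically significant" and Bayes factor cut-offs of 3, 10 and 100, which grade evidence for the alternative only. There is no cut-off for the null. Neither section describes a shift table, a count of out-of-range values or a listing of individual values.

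On the design, Study Design states that "Participants were randomly assigned to one of six groups", and Intervention Details gives the top arm as "Group F: 25 mL HNB in 500 mL NS". No group size is stated. Eligibility Criteria asks for a "stable health condition permitting participation" and excludes liver failure, but sets no entry limits for liver tests or blood counts.

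**The concern.** Liver or blood toxicity can appear as a few people with large changes while the rest of the arm stays put. A comparison of group means handles that pattern badly, for two reasons:

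- The affected participants raise their arm's mean only slightly, and they inflate the error variance against which that mean is judged.
- Haematologic indices have both a low and a high limit, so opposite departures can cancel in a mean.

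The F-test has no direction, and the plan states none for the Bayesian test. At stake is whether anyone reading the planned results would see an individual at 25 mL whose week-5 value is several times the baseline value. The concern is about how values already measured are read. Whether adverse events are collected is a separate matter.

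**Working it through.** The plan gives no figure to reproduce: it states no sample size, SD or power.

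**Inputs from the documents.** Six arms, two visits, two-way threshold p<0.05 or BF10>3, top dose 25 mL (group F).

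**Assumed inputs.** Equal arms of n = 10, 15 or 30; ALT as an example liver test, median 22 U/L, between-person log SD 0.4, visit log SD 0.2; k participants in group F with week-5 ALT of 120-200 U/L. Relative to the median that is 120/22 = 5.5 to 200/22 = 9.1 times.

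**Step 1: reduce the test.** With two visits, the dose-by-time test is a one-way ANOVA F-test on week-5 minus week-0 change, with 5 and 6n−6 degrees of freedom.

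**Step 2: limiting value.** Let k of n participants in one arm have the same rise Δ, large enough that other variation is negligible.

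- Between-arm mean square: (1/5) × n × (kΔ/n)² × (5/6) = k²Δ²/(6n).
- Within-arm mean square: [kΔ²(n−k)/n] / [6(n−1)].
- Ratio: F → k(n−1)/(n−k).

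| n per arm | critical F | k=1 | k=2 | k=3 |
|---|---|---|---|---|
| 10 | 2.39 | 1 | 2×9/8 = 2.25 | 3×9/7 = 3.86 |
| 15 | 2.32 | 1 | 2×14/13 = 2.15 | 3×14/12 = 3.50 |
| 30 | 2.27 | 1 | 2×29/28 = 2.07 | 3×29/27 = 3.22 |

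For one person F tends to 1 whatever the arm size, so a more extreme lone rise is less likely to be flagged. Two equal rises end just below the critical value and three end well above it.

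**Step 3: simulation on the raw scale.** Chance that dose-by-time gives p<0.05:

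| n per arm | k=1 | k=2 | k=3 |
|---|---|---|---|
| 10 | 0.3% | 24% | 99% |
| 15 | 0.6% | 24% | 94% |
| 30 | 1.6% | 19-20% | 80% |

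With nobody affected the rate is about 4.5%, so one marked case makes significance less likely than none. Log-transforming ALT does not rescue k=2 (19%, 17% and 12%).

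**Step 4: all stated rules.** A second simulation used normal change scores (SD 5, 8 or 12 U/L; rises of 60, 100 or 175 U/L). It counted a case as flagged if any of four rules was met: dose-by-time, time, or BF10>3 in group F or pooled. The prior was assumed to be a two-sided Cauchy with scale 0.707, because the plan gives none. One affected participant met some rule in 0-10% of runs at n = 5 to 30. Two with equal rises did so in about 16-31% at n = 10 to 30. BF10>3 within group F occurred in at most 1.6% of runs.

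**Step 5: where the result weakens.** Small arms with two near-equal rises are the exception. At n=5 the limit is 2×4/3 = 2.67 against a critical 2.62, and dose-by-time is significant in 23-54% of runs. At n = 3 to 4 the range is 28% to over 99%. Two unequal rises (60 and 175, or 100 and 175) are flagged in only 0.2-24% at n = 5 to 20.

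**Step 6: would testing counts do better?** Fisher's two-sided test of 2/n against 0/n in control gives p = 0.44-0.49 for n = 5 to 30, and 1/n against 0/n gives p = 1.0. Group F against all other arms combined gives p = 0.17 for one case and 0.023-0.027 for two. A test against control adds little.

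**The case against.** Several stronger readings are tempting, and the documents do not support them.

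- *A reader might infer that such cases would be declared to show no effect.* The Statistical Analysis Plan has no rule for that conclusion. Missing the thresholds means only p≥0.05 and BF10 not above 3.
- *A reader might infer that a significant enzyme rise would count as benefit.* The Bayes factor wording grades evidence that an effect exists, and the sign of the mean change would normally be visible. What stands is that no direction is stated for any outcome.
- *A reader might infer that most participants start in the normal range, so these tests can only show harm.* Eligibility Criteria does not say so. Adults with stable chronic disease and raised enzymes could enter. The dilution result does not depend on this.
- *A reader might infer that the test misses any small cluster.* It does not: with three affected participants it is significant in about 80-99% of trials on the raw scale at n = 10 to 30.
- *A reader might infer that these tests should not be primary.* Study Design names blood biomarkers among the outcomes under study, and an undirected test of change is a legitimate way to examine them.

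It is also fair to say that no significance test reliably detects a single case, and that nothing in the plan forbids tabulating individual values. Both points stand. They make this a gap in planned reporting rather than a wrong choice of test. They do not close it, because the plan commits to no output in which such a case would appear.

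**Conclusion.** The concern holds in a limited form. The only stated reading of liver tests and haematologic indices is by mean change, without reference limits, individual thresholds or direction. At 10 to 30 per arm, under the ALT assumptions above, one markedly affected 25 mL participant makes the dose-by-time test significant in under 2% of trials and two in about 20-25%. Such cases would usually meet no stated evidence threshold. Three would usually be flagged, although a significant test would still not show who was affected.

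The result for one participant rests largely on algebra and held at every arm size tested. The result for two depends on arm size and on how alike the two rises are, and can fail at 3 to 5 per arm. Group size, ALT distribution and size of rise are all assumptions, because the documents give none. The sponsor should make the change, but it does not invalidate the planned analysis.

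**What to change.** Keep the planned mean-change analysis. In the Statistical Analysis Plan, add for liver tests and haematologic indices, by dose group:

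- shift tables of below, within and above the laboratory's reference limits, week 0 against week 5;
- counts above stated multiples of the upper limit, with the multiples chosen and written down by the sponsor;
- the largest individual change in each arm.

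Name the analytes in Outcome Measures so that the tables are defined. Report the direction of any change. State that p≥0.05 or a low BF10 is not evidence of no liver or haematologic harm, and that a significant adverse change is not evidence of benefit. Present the tables descriptively, without tests on the counts. Moving these tests from primary to safety outcomes is optional.

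The cost is some wording and one extra set of tables from data already collected. The tables show individual cases but add no power, and a single out-of-range value in one arm cannot by itself be attributed to dose.

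### The plan names no transformation for the blood markers; if a marker is strongly right-skewed and falls proportionally with dose, an untransformed dose-by-time test can lose about half its power or more

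*Combined protocol and SAP*

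**What the plan says.** Outcome Measures lists the blood profile among the primary outcomes: "Blood profile: inflammatory markers, lipid profile, liver function tests, and hematologic indices". Measurements are taken twice, at weeks 0 and 5. No individual marker is named, and no unit, SD or distribution is given.

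The Statistical Analysis Plan sets one pair of methods for everything. It states "Repeated Measures ANOVA was used to assess within-subject changes (pre- vs post-treatment) and interaction effects between dose and time", and then "The Bayesian paired t-test was applied to complement the ANOVA results". On how outcomes are handled it says only that "each outcome was treated independently without aggregation into composite indices". It mentions no transformation, rank-based method, residual check or outlier rule, and does not state the scale on which blood markers are analysed. Study Design says "Participants were randomly assigned to one of six groups" but gives no number per group.

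**The concern.** Inflammatory markers and liver enzymes are positive quantities. If they vary between people by a multiplicative factor, their distribution is right-skewed and the pre-post change on the raw scale is dominated by the few participants with high values. Those values inflate the error variance of the dose-by-time test, so a real dose effect on a primary outcome may be missed. The paired t-test and its Bayes factor depend on the same values.

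If the sponsor intended to use logs, the plan still has to say so. Otherwise the scale of several primary outcomes is left open until the data have been seen.

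**Working it through.** **Plan's own figure.** There is none to reproduce: no sample size, power, effect size or SD is stated.

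**Inputs from the documents.** Six groups at 0, 5, 10, 15, 20 and 25 mL (Study Design); two time points (Outcome Measures); significance at 0.05 (Statistical Analysis Plan).

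**Assumptions.** Log-normal pre and post values; log-SD σ of 0.5, 0.75 or 1.0; pre-post log correlation ρ = 0.7; n = 15 per arm; effect linear in dose on the log scale, with top-dose ratio r.

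**Step 1: reduce the test.** With two time points, the dose-by-time test is a one-way F-test on change across six arms.

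**Step 2: power on log change.** Scale dose to d = 0, 0.2, …, 1, so Σ(d − mean)² = 0.70. The variance of log change is 2σ²(1 − ρ) = 0.6σ². The noncentrality is λ = n(ln r)² × 0.70 / (0.6σ²). For r = 0.5 the numerator is 15 × 0.4805 × 0.70 = 5.045.
- σ = 0.5: λ = 5.045/0.150 = 33.6, power 99.7%
- σ = 0.75: λ = 5.045/0.3375 = 14.9, power 84%
- σ = 1.0: λ = 5.045/0.600 = 8.4, power 56%

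(5 and 84 degrees of freedom.) Simulation gives 99.7%, 85% and 55%.

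**Step 3: why the raw scale loses.** Take the baseline median as 1. At σ = 0.75 the raw mean shift in the top arm is exp(σ²/2) × 0.5 = 1.325 × 0.5 = 0.66. The saline-arm variance of raw change is 2·exp(σ²)·[exp(σ²) − exp(ρσ²)] = 2 × 1.755 × (1.755 − 1.483) = 0.96, so the SD is 0.98. The standardised effect is 0.66/0.98 = 0.68. On the log scale it is 0.693/0.581 = 1.19.

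**Step 4: simulated power of the dose-by-time test, raw versus log change, 15 per arm.**

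| Top-dose ratio | log-SD 0.5 | log-SD 0.75 | log-SD 1.0 |
|---|---|---|---|
| 0.5 | 87% vs 99.7% | 41% vs 85% | 17% vs 55% |
| 0.7 | 40% vs 59% | 15% vs 28% | 8% vs 16% |
| 2.0 | 99.4% vs 99.7% | 69% vs 83% | 31% vs 55% |

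Relative loss when the marker is halved: (99.7 − 87)/99.7 = 13%, (85 − 41)/85 = 52% and (55 − 17)/55 = 69%. When it is doubled, at log-SD 0.75: (83 − 69)/83 = 17%.

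**Step 5: other settings.**
- 10 per arm, marker halved: about 68% vs 96%, 27% vs 63% and 13% vs 37%.
- Log correlation 0.5, 15 per arm, log-SD 0.75, marker halved: 26% vs 59%.
- Effect set so that the log analysis has 80% power, 5 to 40 per arm, correlation 0.5 to 0.7, proportional decrease: raw power is 59–72% at log-SD 0.3, 38–63% at 0.5, 21–44% at 0.8 and 14–32% at 1.0.
- Constant absolute increase instead of a proportional change (correlation 0.7, 10 and 20 per arm, log-SD 0.3 to 1.0): the raw analysis loses only about 2–17% of power, in relative terms.

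**Step 6: paired t-test.** The ordinary paired t stands in for the Bayesian one, because BF10 rises with |t| at a given n and prior. Top arm halved, 15 per arm: 99.9% vs 100%, 91% vs 99% and 62% vs 90%. The largest loss is (90 − 62)/90 = 31%.

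**Step 7: type I error.** With no effect, the raw-scale dose-by-time test rejects about 4% to 5% of the time.

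**Step 8: adding log baseline as covariate.** The residual variance becomes σ²(1 − ρ²) = 0.51σ² instead of 0.60σ². At σ = 0.75, λ = 5.045/(0.51 × 0.5625) = 17.6 and power is 90%. At σ = 1.0 simulation gives 62%. Type I error is about 5%.

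**The case against.** A reader might infer that the plan prescribes raw-scale analysis and that all inflammatory markers and liver tests thereby lose half or more of their power, in the ANOVA and in the paired t-tests alike. The documents do not support that.

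- **Scale.** The raw scale is inferred from silence. ANOVA on log values would still be repeated measures ANOVA. This stands, although an untransformed analysis is the natural reading of a plan that names no transformation.
- **Skew alone is not enough.** At log-SD 0.5 with the marker halved, the loss is about 13%. With a doubling it stays below half throughout the 15-per-arm table. This stands.
- **Paired t-test.** It loses at most about 31% in the 15-per-arm settings above. In the 80%-power calibration it loses half only at log-SD about 1.2, or at 1.0 with 5 per arm. This stands.
- **Inputs.** Skew, group size and effect are not in the documents. Eligibility asks for stable health and excludes liver failure, and nothing shows which markers, if any, reach log-SD 0.75. One loss figure should not be applied to both inflammatory markers and liver tests. This stands.
- **Weak either way.** With a top-dose ratio of 0.7, even the log analysis has only 28% power at log-SD 0.75 and 16% at 1.0. Logging does not rescue an undersized trial. This stands, but it does not favour the raw scale.
- **Timing.** The plan is written in the past tense, so changing the scale now could itself add analyst choice. This limits how the fix is presented, not whether it is worth making.

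**Conclusion.** The concern holds in conditional form. The plan leaves the scale of primary blood markers unstated and, as written, implies an untransformed analysis. If a marker is log-normal with log-SD of about 0.75 or more and the top dose halves it, the dose-by-time test loses roughly half its power at log-SD 0.75 (41% versus 85%) and more at 1.0 (17% versus 55%), given 15 per arm and log correlation 0.7. With mild skew, a proportional increase, an additive effect or the paired t-test, the loss is smaller. False positives are not inflated, so no spurious claim of benefit follows from the scale.

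The choice is lopsided in favour of logs: if a marker is in fact normal with a coefficient of variation of 10% to 25%, logging it changes power by about 2 points or less in either direction. The change should be made, but it does not replace stating the group size and the target effect.

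**What to change.** In the Statistical Analysis Plan, list by name the inflammatory markers and liver enzymes to be analysed on the natural-log scale. For each, model the log week-5 value by dose group with log baseline as covariate, and report geometric mean ratios versus saline with 95% CI. Compute the Bayes factors for these markers on the same scale. Fix a rule for undetectable values. Settle the marker list before results by arm are examined. If they have already been seen, present the log analysis openly as a sensitivity analysis beside the stated one.

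Two changes are bundled here. Moving to logs gives the main gain (41% to 85% at log-SD 0.75, marker halved). The further step from 85% to 90% comes from the baseline covariate, not from the log.

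The cost is a short addition to the plan, a marker list that does not exist yet, and a re-run of the analysis. Effects become ratios rather than absolute differences, and undetectable values need a substitution.

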## **Statistical Analysis Plan**

Statistical analyses were conducted to evaluate time-related changes and dose-dependent effects.

- Repeated Measures ANOVA was used to assess within-subject changes (pre- vs post-treatment) and interaction effects between dose and time.
- The Bayesian paired t-test was applied to complement the ANOVA results, providing Bayes Factors ( $BF_{10}$ ) that quantify the strength of evidence supporting the treatment effect.
- A p-value < 0.05 was considered statistically significant. BF10 values > 3 indicated moderate evidence, > 10 strong evidence, and > 100 very strong evidence for the alternative hypothesis.
- Data analysis was performed using appropriate statistical software, and each outcome was treated independently without aggregation into composite indices.

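### With only week 0 and week 5 measured, the planned dose-by-time test is a change-score test; adjusting for baseline by ANCOVA would generally be more precise and needs no new data

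*Combined protocol and SAP*

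**What the plan says.** Under Study Design, "Participants were randomly assigned to one of six groups", with doses of 0, 5, 10, 15, 20 and 25 mL. Outcome Measures gives two assessment times, week 0 and week 5, and no visit in between.

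The Statistical Analysis Plan sets two aims: "Statistical analyses were conducted to evaluate time-related changes and dose-dependent effects". For these it states "Repeated Measures ANOVA was used to assess within-subject changes (pre- vs post-treatment) and interaction effects between dose and time". The only other analysis is a pre-post one: "The Bayesian paired t-test was applied to complement the ANOVA results". The plan adds that "each outcome was treated independently without aggregation into composite indices", and sets significance at p < 0.05.

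Neither the protocol nor the SAP uses the baseline value as a covariate. They also give no sample size, standard deviation, pre-post correlation or expected effect.

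**The concern.** The dose-by-time interaction is the only test in the plan that compares the randomised groups. The time main effect and the Bayesian paired t-test both compare participants with themselves before and after, so neither uses the randomisation.

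With two visits, the interaction reduces to comparing mean change across the six groups. A change score subtracts the whole baseline value, as if each unit of baseline carried through to one unit at week 5. When the true relation is weaker, this subtraction adds noise. ANCOVA estimates the relation from the data.

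What is at stake is precision, not validity. With participants divided over six arms, an inefficient test gives wider intervals and a higher chance of missing a real dose effect than the same data would allow. Because each outcome is analysed separately, the loss arises outcome by outcome, and each outcome has its own week 0 value available.

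**Working it through.** **Inputs.** From the documents: six randomised groups, two visits (week 0 and week 5), significance level 0.05, each outcome analysed alone. Assumed, because the documents do not give them: ρ, the SDs s0 and s1, the number per arm (equal arms of 5, 10 or 20), and the effect (rising linearly from 0 at saline to a stated multiple of the baseline SD at 25 mL). The plan has no figure of its own to reproduce.

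**Step 1: the interaction is a change-score test.** With two visits and complete data, the interaction depends on each participant's data only through week 5 minus week 0. On a simulated data set of six arms of 10, the dose-by-time F from the repeated measures ANOVA was 1.51774 and the one-way ANOVA F on change was 1.51774, both on 5 and 54 df. On a second simulated data set both were 2.50368. The identity covers the interaction only, not the time main effect.

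**Step 2: large-sample variance per participant.**
- Change score: s0² + s1² − 2ρ·s0·s1
- ANCOVA: s1²(1 − ρ²)
- Difference: (s0 − ρ·s1)², which is never negative and is zero when ρ·s1 = s0

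These formulas assume the same SDs and the same slope in all arms. With s0 = s1 the ratio of ANCOVA to change-score variance is (1 − ρ²) / [2(1 − ρ)] = (1 + ρ)/2:

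| ρ | 0.3 | 0.5 | 0.7 | 0.8 | 0.9 |
|---|---|---|---|---|---|
| Ratio | 0.65 | 0.75 | 0.85 | 0.90 | 0.95 |
| Variance cut | 35% | 25% | 15% | 10% | 5% |

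**Step 3: the price of estimating the slope.** With n per arm, the ANCOVA variance is inflated by 1 + 1/(6(n − 1) − 2).
- n = 5: 1 + 1/22 = 1.045
- n = 10: 1 + 1/52 = 1.019
- n = 20: 1 + 1/112 = 1.009

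Setting inflation × (1 + ρ)/2 = 1 gives break-even at ρ = 0.913, 0.962 and 0.982. Above those values ANCOVA is slightly worse: at 5 per arm and ρ = 0.95, power is 92.4% for the change score and 91.9% for ANCOVA.

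At 10 per arm and ρ = 0.5, the confidence interval for top dose against saline shrinks by 1 − √(1.019 × 0.75) = 1 − 0.874, about 13%. The same calculation gives about 7% at ρ = 0.7 and 2% at ρ = 0.9.

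**Step 4: power of the 5-df test** (10,000 simulations per setting, equal SDs, effect 0.8 SD at the top dose), change score vs ANCOVA:

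| Per arm | ρ = 0.3 | 0.5 | 0.7 | 0.8 | 0.9 |
|---|---|---|---|---|---|
| 5 | 12 vs 15% | 15 vs 18% | 22 vs 25% | 33 vs 35% | 62 vs 62% |
| 10 | 21 vs 32% | 29 vs 38% | 48 vs 55% | 68 vs 73% | 96 vs 97% |
| 20 | 43 vs 64% | 61 vs 74% | 85 vs 90% | 96 vs 98% | 100 vs 100% |

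At 10 per arm and ρ = 0.5, a 0.5 SD effect gives 13 vs 16% and a 1.0 SD effect gives 46 vs 58%.

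**Step 5: unequal SDs** (10 per arm, 0.8 SD effect).
- s1 = 0.8·s0, ρ = 0.5: in units of s0², the change-score variance is 1 + 0.64 − 0.80 = 0.84 and the ANCOVA variance is 0.64 × 0.75 = 0.48. Power is 35 vs 59%.
- s1 = 1.3·s0, ρ = 0.77: ρ·s1 = 1.001·s0, so there is nothing to gain. Power is 43 vs 42%. At ρ = 0.7 it is 34 vs 34%.

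**Step 6: validity.** With no effect and 10 per arm, both tests rejected close to 5% of the time (4.9–5.3% for change, 5.0–5.1% for ANCOVA). With a true top-dose difference of 0.80, both methods averaged 0.79–0.81. Neither is biased.

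**The case against.** The strongest reply is that nothing here is an error. The planned test is unbiased and holds its type I error, and the repeated measures ANOVA serves both stated aims, whereas ANCOVA addresses only the dose comparison. That is correct. It is why the point is about efficiency and why the repeated measures analysis should stay in the plan.

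The size of the gain in this trial is also unknown. On the assumed settings it runs from more than 20 percentage points of power to nothing, and at 5 per arm it is 0 to 3 points. This stands: the documents do not show which outcomes would benefit. But the trade is lopsided, because the largest loss found was about one point.

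The SAP is written in the past tense. If results are known, replacing a stated valid analysis across many outcomes invites choosing between results. Labelling discloses that risk but does not remove it, so the stated analysis must be reported in full alongside.

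Two technical points also stand. The variance formula assumes a slope common to all arms, and skewed outcomes may need a transformation; both call for a check when the model is fitted. And if the effect really is linear in dose, a 1-df trend test on the planned change scores gains more: 55% and 76% power at ρ = 0.5 and 0.7 (10 per arm, 0.8 SD), against 39% and 55% for the 5-df ANCOVA in the same run. That is a separate improvement and can be combined with baseline adjustment.

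**Conclusion.** The concern holds. The plan's only randomised comparison is, by algebra, a change-score test, and the plan contains no baseline-adjusted comparison. Given randomisation and a common slope, ANCOVA is at least as precise in large samples. In small samples it gives up a little only when ρ is close to 1 or ρ·s1 is close to s0.

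The algebra is certain; the benefit in this trial is not. It would be material for outcomes with low or moderate pre-post correlation and about nil for highly correlated ones. The plan should be changed because the change is cheap and concerns the key comparison, but a result from the planned test would not be invalid.

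**What to change.** For each outcome, make the main group comparison an ANCOVA: week 5 value on week 0 value plus dose group, coded as five indicators against saline. Test dose group from this model and report adjusted mean differences from saline with 95% confidence intervals. State how linearity and the common-slope assumption will be checked. Keep the dose-by-time repeated measures ANOVA as a supporting analysis; it also still serves the aim of describing change over time.

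If results have already been seen, date the ANCOVA, label it a revised analysis, and report the repeated measures ANOVA next to it for every outcome.

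The cost is one residual degree of freedom and a variance penalty of about 5%, 2% or 1% at 5, 10 or 20 per arm. No new data are needed. If results are known, the change is a declared revision of the analysis and not merely a change of wording.

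### No planned analysis compares an individual HNB dose with saline, and the uncontrolled paired test is read as evidence of a treatment effect

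*Combined protocol and SAP*

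**What the plan says.** Study Design describes six randomised arms: "Participants were randomly assigned to one of six groups and received either HNB infusion or normal saline (control) over a 5-week period". It lists the control as the 0 mL dose level, and Intervention Details confirms it: "Group A (Control): 500 mL normal saline". Outcome Measures gives two assessments, at weeks 0 and 5.

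The Statistical Analysis Plan names two analyses:

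- "Repeated Measures ANOVA was used to assess within-subject changes (pre- vs post-treatment) and interaction effects between dose and time".
- A second test, set beside the first: "The Bayesian paired t-test was applied to complement the ANOVA results", with Bayes factors "that quantify the strength of evidence supporting the treatment effect".

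The section sets a 0.05 significance level and Bayes factor cut-offs starting at 3. It names no contrast of a dose with saline, no post-hoc test, no trend test and no multiplicity rule. It does not say whether dose enters as a six-level factor or a linear term, or whether the paired test is run in each arm or over all arms together.

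**The concern.** A trial with five doses and a concurrent control should be able to say which doses differ from control, and by how much. The interaction gives one global answer per outcome. The other named test compares each participant with his or her own baseline and leaves the saline arm out.

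In a pre-post comparison, placebo response, regression to the mean and repeat-measurement effects all count as treatment effect. That matters for outcomes such as blood pressure, heart rate and SF-36. The plan goes further than leaving a gap, because it states that the Bayes factors from this uncontrolled test measure support for the treatment effect. A reader who wants a dose-level result has nothing else to turn to.

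**Working it through.** **Inputs from the documents.** Six arms including saline, two time points, significance level 0.05, lowest Bayes factor threshold 3. There is no sample size, SD, effect size or power figure, so there is no stated figure to reproduce.

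**Assumptions.** Equal arms of 10, 15 or 20; change scores with SD 1; a default Cauchy prior of scale 0.707 for the Bayes factor; paired tests run arm by arm. Results come from simulation with 20,000 to 40,000 trials per setting.

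**1. What the interaction can tell us.** With dose as a factor, its degrees of freedom are (6 − 1) × (2 − 1) = 5, and with two time points it equals a one-way F-test on change scores. A linear dose term would have 1 df. At 15 per arm and an effect of 1 SD, the 5-df test rejects about 76% of the time whether all five doses work or only 25 mL works. A linear term tests a slope and does not identify a dose either.

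**2. No HNB effect, ungated paired tests.** If each active arm is flagged with probability q, then P(at least one of five) = 1 − (1 − q)^5.

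- No shift, p<0.05: 1 − 0.95^5 = 0.226.
- Common 0.5 SD shift, p<0.05: q = 0.291 at 10 per arm gives 0.82; q = 0.565 at 20 per arm gives 0.98.
- The same shift, BF10>3: q = 0.188 gives 0.65; q = 0.397 gives 0.92.

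Over shifts of 0.3 to 0.5 SD and 10 to 20 per arm, the range is 52% to 98% for p<0.05 and about 34% to 92% for BF10>3. With no shift, BF10>3 gives about 9% to 12%.

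**3. No HNB effect, gated on the interaction.** The interaction rejects in about 5% of trials whatever the common shift, so gated paired flags cannot exceed about 5%. Five unadjusted dose-versus-saline tests give about 18% ungated and about 4% gated.

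**4. One dose works.** All arms shift by 0.5 SD, and 25 mL has a real extra 1 SD effect.

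| Per arm | Paired p<0.05 flags at least one of 5–20 mL, among trials with a significant interaction | Dunnett flags one of 5–20 mL, all trials |
|---|---|---|
| 10 | about 75% | about 4% |
| 15 | about 90% | about 4% |
| 20 | about 96% | about 4% |

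The denominators differ, but that does not explain the gap. The interaction is significant in 53% of trials at 10 per arm and 89% at 20, so the Dunnett rate among those trials is at most about 4/0.53 = 7.5% and 4/0.89 = 4.5%.

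BF10>3 is stricter but does not remove the problem. Over all trials, the chance of flagging at least one of the four ineffective doses is 1 − (1 − 0.188)^4 = 0.57 at 10 per arm and 1 − (1 − 0.394)^4 = 0.87 at 20.

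**5. Price of the adjustment.** The two-sided Dunnett critical value at 15 per arm is about 2.56, against 1.99 unadjusted: 2.56/1.99 = 1.29, so intervals are about 29% wider. Power to find at least one dose, for a 1 SD effect at 15 per arm, is 88% (Dunnett) against 76% (F) if all doses work, and 59% against 76% if only the top dose works.

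**The case against.** A reader might infer that the trial makes no controlled comparison at all. The documents do not support that. Saline is the 0 mL level of dose, so the interaction is a randomised, concurrently controlled test and holds its error rate under any shift common to all arms. What is missing is narrower: an estimate or test for each individual dose against saline.

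A reader might also infer that the plan prescribes arm-by-arm paired tests and calls a dose effective on that basis. It has no such decision rule. Arm-by-arm use is an assumption here, as are the 5 df. If the paired test pools all arms, it says even less about any one dose.

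The strongest objection concerns the gate. The plan presents the paired test as complementing the ANOVA. If dose claims follow only a significant interaction, false claims with no HNB effect at all are already held near 5%, and the 18% for unadjusted contrasts falls to about 4%. That stands, and the ungated figures should be quoted only with that label. The plan, however, states no gate, and a gate gives no protection once one dose works (step 4).

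Finally, the plan's paired test is Bayesian, so the p<0.05 figures overstate what its own threshold would flag. The Bayes factor figures are lower but remain large whenever there is a common shift.

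**Conclusion.** The concern holds in this form: the plan provides a valid global test but no estimate or test of any single dose against saline, and it reads an uncontrolled pre-post statistic as evidence of a treatment effect. That reading is a stated rule that should change, not merely an omitted detail.

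The size depends on assumed arm sizes, shift, effect and prior, none of which the documents give. The structural point does not depend on them: neither named test identifies a dose that differs from saline. The most relevant figure is the case where one dose works, because there a significant interaction does not stop paired tests from crediting ineffective doses. The global result stays usable; dose-level claims from this plan would not be.

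**What to change.** In the Statistical Analysis Plan, add for each outcome:

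- The mean difference at week 5 between each HNB dose and saline, adjusted for baseline, from one model containing all six arms, with Dunnett-adjusted p-values and simultaneous 95% confidence intervals.
- A statement that any claim that a dose differs from saline rests on this comparison only.
- A statement that within-arm pre-post changes and paired Bayes factors are descriptive and are not evidence of a treatment effect.
- A statement that the overall dose-by-time test is kept and does not gate the Dunnett comparisons. Keeping it matters because it has more power when only one dose works.

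The cost is SAP wording and one further model output per outcome, with no new data. There are three downsides. Intervals are about 29% wider than unadjusted ones. Error is controlled within each outcome only, not across the many primary outcomes. The plan is written in the past tense, so if data have already been analysed the added comparisons should be labelled post hoc. The simulations used change scores, so the power figures will not carry over exactly to the baseline-adjusted model.
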